**Flowchart**

Activity / Endpoint	Baseline 	Post-diagnosis period (days)					End of study at hospital discharge or in-hospital death after ICU discharge
		1	3	5	7	ICU discharge or death on ICU after day 7	
Confirm inclusion criteria	x						
Provision of informed consent 	x						
Demographic data collection (incl. ethnic origin)	x						
Risk factors (vaccination status, asplenia) and comorbidities	x						
Estimated time of SAPF onset (hours)	x						
Mortality prediction (APACHE II/SAPS II  or PRISM III  score)	x						
Morbidity assessment (SOFA  /PELOD  score)	x	x	x	x	x		
Laboratory parameters (hematology, coagulation, inflammation)	x	x	x	x	x		
Purpura lesion assessment (c.f. eCRF)	x	x	x	x	x		
Vasopressor use record	x	x	x	x	x	x	
Site, source and origin of infection (including viral)							x
Concomitant causal, supportive and adjunctive treatment (c.f. eCRF)		x	x	x	x	x	
Cumulative dose of blood products and anti-coagulant treatment		x	x	x	x	x	
Antimicrobials		x	x	x	x	x	
Days in ICU							x
Days on mechanical ventilation							x
ECMO and circulatory support systems		x	x	x	x	x	
Days/type on renal replacement therapy							x
Purpura-related surgery (fasciotomy, debridement, amputation)							x
In-hospital mortality assessment		x	x	x	x	x	x
Days in hospital							x
Adverse drug reactions							x

 admission at ICU; according to local regulations APACHE II/SAPS II and SOFA scores will be used in patients aged above 16 PRISM III and PELOD scores will be used in patients aged below 16

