#### 8.4. Data sources

Registry subjects will be identified by the participating centers. The recruitment will be primarily based on the concomitant presence of clinical signs of sepsis and *Purpura fulminans*. Clarification of the underlying etiopathogenesis will be performed *post hoc*, upon collection of additional clinical and laboratory data.

Data capture comprises assessment at baseline and at several intervals of 24 (initially) and 48 (subsequently) hours for an overall period of 7 days, while in ICU. A final appraisal of the patient's status will take place at the time point of discharge from the hospital.

The exposure to individual therapeutic agents will be deduced from doses and frequency of application during the period spent in ICU.

The influence of potential confounding variables and effect modifiers (e.g. concomitant anticoagulant medication, fluid resuscitation, renal replacement therapy etc.) will be extrapolated from the corresponding specific entries in the eCRF.

The outcome indicators have been previously validated and are routinely used.

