#### 8.6. Data management

Individual data will be collected in accordance with the flowchart by means of electronic Case Report Forms (eCRF) and transmitted by remote data entry to the server of the Center for Clinical Studies of the Jena University Hospital. The local user authentication is ensured by password-protected logins. A role-based hierarchical security structure warrants multi-tier prevention of unauthorized access. The communication between the participating site's workstation and the server is encrypted. Data processing employs the software OpenClinica, which fulfills the regulatory requirements (GCP, 21 CFR Part 1).

Data management will resort to electronic applications. The anonymity of data is warranted in the course of evaluation. A first plausibility check will take place during raw data input in the eCRF at the investigator site, with missing or implausibly aberrant values signaling imminent correction requirement. A further verification of plausibility and consistency will be conducted by applying a controversy-detection algorithm. Permission for data corrections will be conferred to a restricted number of authorized study personnel (e.g. site investigator, study nurse, data manager). A final plausibility check will take place upon receipt of the reply to queries and the eCRFs bearing all annotated modifications.

falsch

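### As written, the flowchart gives patients who die on ICU no scheduled entry for infection source or purpura-related surgery, although the text promises these records for everyone

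*Combined protocol and SAP*

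**What the plan says.** The flowchart in section 8.2 has two closing columns. One is headed "ICU discharge or death on ICU after day 7" and the other "End of study at hospital discharge or in-hospital death after ICU discharge". The rows "Site, source and origin of infection (including viral" and "Purpura-related surgery (fasciotomy, debridement, amputation" each carry a single tick, in the second of these. Five other summary rows are ticked only there: ICU days, hospital days, ventilation days, renal replacement days and adverse drug reactions. The mortality row is ticked on days 1, 3, 5 and 7 and in both closing columns.

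Section 8.6 makes this table the basis for collection: "Individual data will be collected in accordance with the flowchart by means of electronic Case Report Forms (eCRF". Section 8.4 says that the final appraisal "will take place at the time point of discharge from the hospital" and does not mention death.

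Elsewhere the intention is broader. Section 8.2 states that the causal pathogen will be identified, and section 8.3 that surgical interventions will be described. Neither limits this to patients who leave ICU alive, and neither gives a time point. Section 8.4 adds: "Clarification of the underlying etiopathogenesis will be performed" after the event, once further data are in.

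**The concern.** The two headings separate death on ICU from later in-hospital death and attach the end-of-study rows only to the latter. A site that follows the table has a place to record that an ICU patient died, but no scheduled place for what infected the patient or what surgery was done. Missingness would then depend on the outcome.

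The pathogen matters most. Its relation to the disease is part of the first research objective in the Abstract, it is a listed endpoint, and section 8.2 names it as a stratifier of outcomes. If ICU deaths drop out, the pathogen distribution leans towards organisms that patients survive, and pathogen-specific mortality is understated.

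Surgery is a weaker case. The listed endpoint is reconstructive surgery, meaning amputations and skin grafts. The flowchart row covers fasciotomy, debridement and amputation, so only amputation is common to both. A blank read as no surgery would undercount. A blank left out would make the figure describe mainly patients who left ICU alive.

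**Working it through.** **The schedule, by route out of hospital**

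| Route | Closing column that applies | Infection source and surgery ticked? |
|---|---|---|
| Discharged alive | End of study | Yes |
| Death on the ward after ICU | End of study | Yes |
| Death on ICU after day 7 | ICU discharge or ICU death | No |
| Death on ICU by day 7 | None (mortality status on days 1, 3, 5, 7 only) | No |

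Neither row is ticked at baseline or on days 1 to 7, so no earlier entry fills the gap. Sections 8.2, 8.3 and 8.4 give no recording point for ICU deaths. Section 8.7 states no rule for missing data.

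**Illustration of size.** The plan gives no figure to reproduce.

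Inputs from the plan:
- About 50 patients per year for 3 years (Abstract), so N = 3 × 50 = 150.
- Mortality above 50% (Abstract and section 6), set here at 50%, so D = 75 deaths.

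Assumptions that are not in the plan:
- s, the share of deaths that occur on ICU: 50% to 90%.
- q, the share of ICU deaths left without an entry: 0%, 25%, 50% or 100%.

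Formulas: deaths without an entry L = D × s × q; share of deaths among patients with an entry = (D − L)/(N − L). The true share is 75/150 = 50%.

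| q | L at s = 50% | Share of deaths | L at s = 90% | Share of deaths |
|---|---|---|---|---|
| 0% | 0 | 75/150 = 50% | 0 | 75/150 = 50% |
| 25% | 9.4 | 65.6/140.6 = 47% | 16.9 | 58.1/133.1 = 44% |
| 50% | 18.75 | 56.25/131.25 = 43% | 33.75 | 41.25/116.25 = 35% |
| 100% | 37.5 | 37.5/112.5 = 33% | 67.5 | 7.5/82.5 = 9% |

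At the upper enrolment that section 8.5 allows (70 + 100 + 100 = 270, hence 135 deaths), q = 100% gives L = 67.5 to 121.5, with the same percentages.

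The share of deaths among patients with an entry is not a planned estimand. It only shows how far the patients with a pathogen record could differ from the whole cohort. The error in the pathogen distribution or in surgery frequency cannot be computed, because the plan does not say how either differs between ICU deaths and other patients.

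**The case against.** The best defence is that the heading is loose shorthand. Read literally, it would also leave ICU days and hospital days unrecorded for every ICU death, which a registry with in-hospital mortality as its first-listed endpoint is unlikely to intend. Section 8.4 is loose too, since it omits the ward deaths that the flowchart includes. Pathogen and past surgery can be taken from the chart after death. This is a fair account of what was probably meant, and sections 8.2 and 8.3 support it. It does not remove the error: if the column is meant for everyone, its heading and section 8.4 are wrong.

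There are also safeguards. Section 8.6 provides for "missing or implausibly aberrant values signaling imminent correction requirement", followed by queries and a final check. Section 9 makes replacement of the ID numbers wait until data management has confirmed that relevant information is complete. These may recover entries. They work less surely on a form that the schedule never made due, and section 8.8 does not foresee monitoring visits by default.

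The surgery part is rightly discounted. Sections 8.3 and 8.9 place reconstructive surgery late in the course, which helps explain the late column and suggests that fewer ICU deaths would have had it.

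A reader might infer that adverse drug reactions are lost in the same way. Section 10 gives them a separate reporting route, so no conflict is shown there.

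**Conclusion.** The schedule contradicts the text, and the contradiction falls along the line between ICU deaths and other patients. If sites follow it literally, pathogen data would be selectively missing for ICU deaths; for surgery data this is less certain. The illustrative range is 0 to 68 of 75 deaths without an entry at N = 150. It rests wholly on the assumed s and q, and zero is the result if sites close the end-of-study form for every patient.

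Two stronger readings are not supported:

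- *That data have been lost.* The eCRF is not among the documents, and queries or the completeness confirmation may fill gaps.
- *That the mortality comparison is biased.* Unadjusted mortality is unaffected, because death is recorded on its own row. In the logistic model of section 8.7, pathogen is an optional covariate. Harm would need it to be included and patients without it to be dropped. Even then the treatment odds ratio could stay consistent if missingness depended on death alone, with a loss of precision. Bias would require missingness to depend also on treatment or severity.

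The point is therefore a defect in the written schedule that is worth correcting, not a demonstrated bias.

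**What to change.** 1. Re-head the last flowchart column *End of study: hospital discharge or any in-hospital death (ICU or ward, at any time)*, and require all its rows for every patient.
2. In section 8.4, place the final appraisal *at discharge from hospital or death*.
3. Set the eCRF so that any recorded death opens the end-of-study form, if it does not already do so.
4. Report completeness of pathogen and surgery data separately for deaths and survivors.

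The cost is a short protocol amendment and possibly one eCRF trigger, with no new visit or procedure. For patients already entered, these two items should be checked for ICU deaths at the completeness confirmation in section 9, before ID numbers are replaced. Where replacement has already taken place, remaining gaps may have to be reported as missing.

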### 8.3. Variables

The selection of the endpoint all-cause in-hospital mortality is justified, in view of the exceptional severity of the disease *per se* and considerable risk associated with the subsequent management of its late sequelae (e.g. reconstructive surgery). On a case-by-case basis, a comparison with the probability of a lethal outcome, as defined by the APACHE II/ SAPS II or PRISM III score, will be made.

Changes in morbidity (as assessed by the SOFA or PELOD indices) will be presented by the difference between scores measured at admission and after 1, 3, 5 and 7 days upon being diagnosed with SAPF ( $\Delta$ SOFA, dPELOD), as well as by the mean total score (SOFA, PELOD) recorded over the observation period of 7 days.

Records will also include description of imminent surgical interventions (during the SAPF treatment), as well as reconstructive measures (skin grafting, amputation).

The sepsis-inducing pathogen and the primarily affected organ will be identified by the results of microbiological examinations and in accordance with clinical manifestations.

Further endpoints comprise the length of stay in the ICU and the total duration of hospitalization (including time of post-SAPF therapy).

Changes in hematological, coagulation and inflammatory parameters will be monitored at selected intervals across the treatment and serve as biomarkers of treatment efficacy or surrogate endpoints, as follows:

- Thrombocyte counts
- Leukocyte counts
- Hemoglobin
- Prothrombin time (PT)
- Activated partial thromboplastin time (aPTT)
- Fibrinogen
- D dimers
- Thrombin-Antithrombin complex (TATc)
- Protein C activity
- Antithrombin III activity
- C-reactive protein (CRP)
- Procalcitonin (PCT)
- Interleukin 6 (IL-6)

Several of these parameters have been used in clinical studies and shown significant changes in the course of therapeutic interventions in sepsis and Purpura fulminans [Bernard et al., 2001; de Kleijn et al., 2003; Schellongowski et al., 2006; Shorr et al., 2008].

Laboratory indices of organ dysfunction are confined to measurements of

- Glucose
- Lactate
- Creatine kinase

Recording of adverse events related to the treatment of SAPF is left at the discretion of the local site investigator (c.f. comment in 9.9. *Limitations of research methods*); the emphasis is laid on

- bleeding incidents
- thrombotic events

#### 8.4. Data sources

Registry subjects will be identified by the participating centers. The recruitment will be primarily based on the concomitant presence of clinical signs of sepsis and *Purpura fulminans*. Clarification of the underlying etiopathogenesis will be performed *post hoc*, upon collection of additional clinical and laboratory data.

Data capture comprises assessment at baseline and at several intervals of 24 (initially) and 48 (subsequently) hours for an overall period of 7 days, while in ICU. A final appraisal of the patient's status will take place at the time point of discharge from the hospital.

The exposure to individual therapeutic agents will be deduced from doses and frequency of application during the period spent in ICU.

The influence of potential confounding variables and effect modifiers (e.g. concomitant anticoagulant medication, fluid resuscitation, renal replacement therapy etc.) will be extrapolated from the corresponding specific entries in the eCRF.

The outcome indicators have been previously validated and are routinely used.

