Research question and objectives	
 
Systematic acquisition, analysis and dissemination of information on incidence and prehospital/inhospital course of Purpura fulminans, (possible long-term follow up) and its relation to infectious agents (e.g. meningococcemia, streptococcus etc.)
 
Systematic acquisition, analysis and dissemination of information on current management of PF (sepsis bundles and replacement strategies – protein C, AT, etc.)
 
Systematic acquisition, analysis and dissemination of information on outcomes (morbidity, mortality) of PF with current management strategies, stratified for use or non-use of protein C
 

Design	Prospective multicenter registry derived from systematic data collection on the incidence and treatment of sepsis-associated Purpura fulminans
Population	Patients diagnosed with Purpura fulminans associated with severe sepsis

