## **8. Research methods**

### **8.1. Study design**

The registry comprises prospective, open-label data collection on the current state of incidence and management of SAPF, regardless of the etiopathogenic background. Using appropriate statistical techniques, specific emphasis will be laid on the comparison of outcomes in therapeutic approaches including or avoiding supplementation with Protein C formulations.

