#### 8.5. Study size

Earlier reports on the incidence of SAPF [Darmstadt, 1998; Nicolas and Debonne, 2002] were based on the association of the condition with meningococcal sepsis. Conceivably, these data hardly permit extrapolation to the contemporary situation, which has substantially changed after the introduction of meningococcal vaccination [Maat et al., 2007]. Depending on the number of participating centers, a realistic forecast envisages the recruitment of 50 to 70 adult and pediatric patients during the first year of the registry, with subsequent possible increase to 100 per year. In view of the spread of meningococcal vaccination among children and adolescents, the expected proportion of adult patients might eventually exceed 50 %.

With regard to the relatively limited projected study size, and with regard to the lack of a uniform treatment concept for SAPF, demonstration of differences between individual treatment paradigms might require dichotomization (e.g. use vs. omission of Protein C supplementation) and could be applicable only to selected endpoints.

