## 8.7. Data analysis

A binary logistic regression model will be fitted for the all-cause in hospital mortality to compare the efficacy of the different treatments (e.g. with or without Protein C supplementation). To adjust for confounders, causal pathogen, baseline Apache II (PRISM III) score, laboratory parameters, age, sex, co-medication etc. can be included as covariates in this model.

Consecutive changes in SOFA or PELOD scores ( $\Delta$ SOFA, dPELOD) at individual post-diagnosis intervals and their mean values calculated for the observation period of 7 days will be compared to the scores determined on admission (baseline). Changes in these organ failure indices will be examined by means of

- Paired samples T-test
- Linear model with morbidity score baseline adjustment and alternative co-variables (e.g. hematological, coagulation or inflammatory parameters)

Explorative analysis without correction and with a pre-set level of significance of 0.05 will be conducted as well.

All endpoints will be subjected to descriptive statistical analysis with determination of 95-percent confidence intervals. Between-group comparisons will be preceded by distribution analysis (Shapiro-Wilk Test of normality). Depending on the data distribution, *post hoc* processing will involve either parametric (one-way ANOVA, T test) or non-parametric (Kruskal-Wallis, Mann-Whitney U-test) approaches.

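### Protein C exposure is read from the whole ICU stay, with no start window and no rule for deaths before a first dose; if those deaths count as unexposed, a timing bias component favours Protein C

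*Combined protocol and SAP*

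**What the plan says.** Section 8.4 (Data sources) defines exposure: "The exposure to individual therapeutic agents will be deduced from doses and frequency of application during the period spent in ICU". The third objective in the abstract concerns "outcomes (morbidity, mortality) of PF with current management strategies, stratified for use or non-use of protein C". Section 8.1 puts emphasis on the "comparison of outcomes in therapeutic approaches including or avoiding supplementation with Protein C formulations". Section 8.5 says that showing differences between treatments might need "dichotomization (e.g. use vs. omission of Protein C supplementation"), so there the split is an example and not a fixed rule.

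For the analysis, 8.7 states: "A binary logistic regression model will be fitted for the all-cause in hospital mortality to compare the efficacy of the different treatments". Covariates are optional: besides causal pathogen and the baseline severity score, "laboratory parameters, age, sex, co-medication etc. can be included as covariates in this model".

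Two time origins are in use. The flowchart in 8.2 footnotes baseline as ICU admission, while its later columns are headed as days after diagnosis. Section 8.3 likewise takes the "difference between scores measured at admission and after 1, 3, 5 and 7 days upon being diagnosed with SAPF". The flowchart row "Cumulative dose of blood products and anti-coagulant treatment" is first ticked at day 1 and has no baseline tick. In-hospital mortality is also ticked from day 1. Severity scores, laboratory values and vasopressor use are ticked at baseline.

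No section gives a latest start for counting a patient as treated, a landmark, a time-dependent exposure, or a classification for patients who die before any dose. The limitations in 8.9 do not mention treatment timing.

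**The concern.** On a use/non-use split over the ICU stay, a patient must live to the first dose to be a user. A patient for whom Protein C was intended, but who died first, moves to the comparison group and takes the death along. This happens even if Protein C does nothing. Group membership is then set partly by events after baseline, so a baseline severity score cannot correct it. Section 6 describes a rapidly evolving disease with mortality above 50%, so early deaths are plausible.

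Section 8.7 also allows co-medication as a covariate without limiting it to what was given before Protein C. Later co-medication may be a consequence of treatment or of early survival.

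Mortality with and without Protein C is a stated objective. Sections 7 and 11 say that the results will feed recommendations on Protein C use and on therapy, updated from twice-yearly evaluations. If the rule is left open, it can be chosen after the data are seen, and readers could not separate the timing artefact from any effect or from confounding.

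**Working it through.** The documents give no power, effect size or timing figure, so there is no figure of the plan's to reproduce. The check asks what the comparison would show if Protein C had no effect.

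**Inputs from the documents.** Mortality above 50% (section 6; 50% used). About 50 patients a year for 3 years (abstract), so 50 × 3 = 150. Level 0.05, which 8.7 states for its explorative analysis only.

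**Assumptions (not in the documents).** Half of patients are intended for Protein C, regardless of prognosis. Delay to first dose is exponential with mean m = 6, 12 or 24 h. Time to death among those who die is exponential with median D = 1, 2 or 4 days.

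**Reading A: early deaths count as unexposed.** Let q be the probability that an intended patient who will die does so before the first dose:

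q = (ln 2/D) / (ln 2/D + 1/m).

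Users comprise 0.25(1 − q) deaths and 0.25 survivors. Non-users comprise 0.25(1 + q) deaths and 0.25 survivors. Hence OR = (1 − q)/(1 + q). At the centre (m = 12 h, D = 48 h), q = 0.0144/(0.0144 + 0.0833) = 0.148 and OR = 0.852/1.148 = 0.74.

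**Reading B: patients who die before the day-1 dose entry (taken as 24 h) have missing exposure and drop out.** Only later deaths can be misplaced, with probability q′ = q·exp(−24/m), and OR = (1 − q′)/(1 + q′). At the centre, q′ = 0.148 × 0.135 = 0.020 and OR = 0.96.

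| m | D | q | OR, reading A | q′ | OR, reading B |
|---|---|---|---|---|---|
| 6 h | 4 days | 0.042 | 0.92 | 0.001 | 1.00 |
| 12 h | 2 days | 0.148 | 0.74 | 0.020 | 0.96 |
| 24 h | 1 day | 0.409 | 0.42 | 0.151 | 0.74 |

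The first and last rows are the extremes of the nine combinations. In simulated registries of 150, false positives at 0.05 under reading A run from about 6% to 73% (centre 14%). The 73% is the single corner of 24 h and 1 day. Under reading B they run from about 5% to 12% (centre 5%).

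**Check without timing assumptions.** Let a share e of all patients die before a first dose and count as unexposed, half of the rest receive Protein C, and total mortality be 0.50. Mortality with Protein C is (0.50 − e)/(1 − e). Mortality without is [e + 0.5(0.50 − e)]/[e + 0.5(1 − e)]. For e = 5%: 47.4% against 52.4%, OR 0.82. For e = 10%: 44.4% against 54.5%, OR 0.67.

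**Does severity adjustment help?** Simulated, assuming that severity raises the log-odds of death by 1.0 and of intended Protein C use by 0.5 per SD, with reading A. With severity measured perfectly, the adjusted OR for intended treatment is about 1.00, so confounding is gone, yet the adjusted use/non-use OR is still 0.41 to 0.92. With a score of reliability 0.7 or 0.5 it is 0.46 to 1.06 or 0.50 to 1.14, so the net sign is not determined.

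**Day-1 landmark.** Classify by first dose within 24 h, among patients alive at 24 h. Without confounding the null OR is 0.99 to 1.00. Under the confounding above, at reliability 0.7 or 0.5, it is 1.10 to 1.15 or 1.17 to 1.24. In 9 of those 18 combinations it lies further from 1 than the use/non-use OR (at 12 h, 2 days and reliability 0.5: about 1.2 against about 0.9).

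**Cost of the landmark.** The share of deaths before 24 h is 1 − 2^(−24/D) with D in hours: 50%, 29% and 16% for 1, 2 and 4 days. Times 0.50, that is 25%, 15% and 8% of patients. Among intended users alive at 24 h, exp(−24/m) = 2%, 14% or 37% are not yet treated. A true OR of 0.50 then reads about 0.51 to 0.59 at the landmark, against about 0.23 to 0.46 for use/non-use under reading A.

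**The case against.** The plan nowhere says that early deaths are unexposed. With the first dose entry at day 1, a death before it may simply have no exposure record and leave the model. That stands: it is reading B, and it shrinks the centre from 0.74 to 0.96. But the plan does not say which reading applies, and reading B is not free of bias when dosing is slow.

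Section 8.4 does name a period, the ICU stay. A reader might infer that the plan has no exposure window at all; that is not so. What is missing is a start window.

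A reader might also infer that the registry's final estimate will favour Protein C. The documents do not support that. Treatment is the physician's choice (section 9), and if sicker patients receive Protein C, confounding acts the other way and can offset or reverse the timing component.

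Consent before enrolment (section 9) may keep some very early deaths out, although local deviations are allowed. If deaths in the first 12 h were never enrolled, the OR under reading A would be 0.99 to 0.60 (centre 0.90).

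Finally, the landmark is not uniformly better. It discards deaths in a small registry, and its net error can be larger where severity is poorly measured. That stands, and it argues for showing the landmark beside the use/non-use result, not in its place. The eCRF, which may hold dose times, is not among the documents.

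**Conclusion.** The point holds conditionally and should be fixed. Exposure over a survival-dependent period, a use/non-use split and a logistic model without a time axis leave room for an immortal-time component. Wherever deaths before a first dose count as no Protein C, that component favours Protein C, and baseline adjustment does not remove it.

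Its size cannot be read from the documents. Assuming no true effect, no confounding, 50% mortality, half intended for Protein C, a mean delay of 6 to 24 h and a median time to death of 1 to 4 days, the OR is 0.92 to 0.42 (centre 0.74) on reading A and 1.00 to 0.74 (centre 0.96) on reading B. With prompt dosing and late deaths it is small on either reading. The net direction of the final estimate is not determined. Confidence is medium, because the timings are assumed and the eCRF is not visible.

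**What to change.** In 8.7:

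1. State one time zero for the treatment comparison that matches when the baseline covariates are measured. The flowchart's baseline is ICU admission, while its days count from diagnosis, so the two must be reconciled. State how Protein C given before time zero is classified, since 8.4 counts only ICU doses.
2. Do not rest the mortality comparison on ever-use in ICU alone. State how deaths before a first dose are classified there. Add a pre-stated landmark analysis that classifies Protein C by whether it was started by the day-1 assessment, in patients alive then. Report it beside the use/non-use result, with the number of deaths before day 1, split by treatment received only if the eCRF holds that.
3. Adjust only for factors fixed before treatment: age, sex, admission APACHE II/SAPS II or PRISM III, baseline laboratory values, baseline vasopressor use, and causal pathogen where recorded. Describe later co-medication, but do not adjust for it.
4. Add a time-dependent exposure model only if the eCRF holds the time of first dose.

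The cost is about a paragraph, because dose and mortality are already ticked at day 1 and the covariates at baseline. The text should state the drawbacks. Under the assumptions above, the landmark leaves out 8% to 25% of patients, which is 16% to 50% of deaths. It is conditional on day-1 survival and somewhat dilutes a real effect. It removes the timing bias but not confounding by indication. This is an analysis rule and does not affect how patients are treated.
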